1.2 Project Personnel and Collaborators

The Principal Investigator will complete initial planning, invite participants to participate in the project, manage all assessment and final appointments, analyse the data, write the initial report and disseminate the results.

The first co-applicant will contribute to initial planning, provide support for the application, provide advice on managing all financial aspects, provide advice on other clinical and research aspects, and contribute to the write-up and dissemination of results. The second and third co-applicants will provide support to the research design and write-up. Audiologists from the Wrexham Maelor Hospital Audiology Department will assist with data collection and highlighting possible participants to the Principal Investigator.

1.3 Identification of Project

One of the main challenges faced by people with hearing loss is understanding speech in noisy environments. Hearing aids can be of some benefit in these situations; however, in isolation they are unable to fully overcome the problem. If the hearing-impaired listener is unable to understand conversations in everyday listening environments they risk becoming socially withdrawn and isolated.

Auditory training involves structured practice listening to a variety of stimuli and is gaining support as an alternative to hearing aids or a supplementary intervention. Many of the auditory training programmes currently available are administered using a computer which may not be appropriate for many older hearing-impaired adults who do not have access to computers. There is therefore a need to develop a non-computerised auditory training intervention which can be delivered easily in the person's home.

The research question is; does repeated practice improve speech perception in everyday challenging listening environments for experienced adult hearing aid users? The study aims to explore whether a novel auditory training programme, which involves having conversations in the presence of a competing speaker, can improve patient outcomes. Hearing aid users will complete a baseline speech and cognition assessment and then undertake a four-week training programme at home. Their speech perception and cognitive abilities will then be evaluated again.

2 Research Protocol

2.1 Research Aims and Objectives

This study will form a randomised controlled trial (RCT) investigating the effect of a novel auditory training intervention. The primary aim is to explore whether the training programme can improve speech intelligibility in noise for experienced adult hearing aid users. A secondary aim is to investigate the effect of training on self-reported listening and cognitively demanding tasks, as cognition has been shown to mediate speech perception.

2.2 Literature Review

2.2.1 Limitations of Hearing Aids in Challenging Listening Environments

It has long been established that people with hearing impairment have greater difficulty understanding speech in challenging listening environments than do normally hearing listeners. Listening to speech in background noise is one of the main complaints among hearing aid users. In the EuroTrak survey (Hougaard and Ruf, 2011), "use in noisy situations" showed the lowest levels of satisfaction among UK hearing aid users, with a net satisfaction score of just 23%. While modern hearing aids can improve the audibility of the speech signal they are unable to eliminate unwanted background noise or overcome suprathreshold deterioration in the hearing system such as declining central auditory processing, impaired frequency and temporal resolution (Plomp, 1986). As such, the signal received by hearing-impaired listeners is degraded to such an extent that perception of speech in background noise is often severely affected. Hearing aids alone are unable to provide sufficient improvement in this challenging listening environment to give high levels of user satisfaction. These low levels of satisfaction may lead to low use of hearing aids which costs the NHS valuable resources every year. The difficulties that listeners face also make it more difficult for them to participate in social interactions which may result in them becoming socially withdrawn and isolated (Shinn-Cunningham and Best, 2008).

2.2.2 Auditory Training

Hearing aids are not the only intervention available to audiologists. As well as hearing aids, the Quality Standards for Adult Hearing Rehabilitation Services (Scottish Government, 2009) also advocate the use of non-instrumental interventions in individual management plans. Auditory training has been used for a number of years as part of an aural rehabilitation programme for patients with hearing loss (Musiek, 2006). It can be described as a process of teaching the brain to listen through active engagement with sounds, and results in improvements on the trained task (Henshaw and Ferguson, 2013b). However, for auditory training to be an effective intervention for people with hearing loss, any improvements in trained tasks need to generalise to functional benefits in real-world listening. The most direct way to achieve this is to train on a task for which improvements are most important to the individual.

Auditory training as a management option is most commonly used in children and adults who have been diagnosed with Auditory Processing Disorder. Patients with Auditory Processing Disorder often have normal hearing thresholds and the effects of auditory training on patients with peripheral hearing difficulties have been less consistently researched. Auditory training may take the form of analytic training, whereby bottom-up processes such as phonetic or temporal perception are directly trained, or synthetic training focusing on improvement in spoken language comprehension (Musiek et al., 2007). Reports in the literature as to the effectiveness of each approach are mixed. In a systematic review of the literature, Sweetow and Palmer (2005) concluded that synthetic training. However, phoneme discrimination training (analytic) has more recently been linked to improvements in cognitive processing which may give additional benefit to patients in complex listening environments (Ferguson et al., 2012).

Auditory training programmes are designed in line with learning theory. Wolfle (1951) learning theory states that in order for a training task to be effective the participant must be actively involved in the task. There should be variation in the practice task to maintain motivation and adaptation. Wolfle also states that the duration of the practice time should be suitable relative to the task that is to be learned. The most important factor of learning theory is that immediate feedback is available as to the participant's performance on the task. Sweetow and Sabes (2006) also note that a comprehensive training programme should be cost-effective, interactive, practical and easily accessible. Ideally the training programme should be sufficiently challenging as to maintain interest and provide scope for learning, however not so difficult as to restrict learning opportunities, induce fatigue and discourage participation. Reinforcement and feedback on task performance should be provided throughout.

2.2.2.1 Auditory Training Programmes Currently Available

Based on these principles a number of structured auditory training programmes are commercially available. A summary of commonly used programmes is given in Table 1. The LACE training programme is currently given to some Hearing Therapy patients in Betsi Cadwaladr University Health Board in order to improve their listening skills. Although these programmes are often used in the UK, Phonomena is the only

programme which was designed and developed here. This means that with other programmes, the speech stimuli used often have American accents which can increase the listening demand for users (Mattys et al., 2012). As can be seen in Table 1, training programmes require a large amount of commitment from the user to practice the tasks a few times per week for long periods of time. A systematic analysis by Henshaw and Ferguson (2013a) showed that compliance with programmes during research studies was relatively high (between 70 and 80%) however these results were not consistent with a clinical study involving users of the LACE programme in America where programme compliance was only 30% (Sweetow and Sabes, 2010). This suggests that the compliance rates shown in small scale research projects may not be representative of the clinical picture at large. While a computerised programme is beneficial as it can be carried out at home while providing real-time training information to the monitoring clinician via the internet, this delivery method may not be appropriate for all hearingimpaired listeners. In a survey of adults aged 50-74 years, Henshaw et al. (2012) showed that computer use varied with age. Computer and internet use was 81.0% and 60.9% respectively for the younger adults (aged 50-62 years) but reduced to 65.4% and 29.8% respectively for the older adults (aged 63-74 years). The mean age of patients attending for hearing reassessment in Betsi Cadwaladr University Health Board is 73.37 years. While these statistics do not discount computerised service delivery as an option, particularly in future as computer literacy increases, alternative delivery methods need to be available for many hearing-impaired listeners.

2.2.2.2 Effects of Auditory Training

Studies evaluating the effect of LACE have shown positive results on a range of measures in the US (Sweetow and Sabes, 2006; Song et al., 2012; Olson et al., 2013) however the effectiveness of the programme for our patient group has yet to be evaluated. Following a four-week training programme using LACE statistically significant, and more importantly clinically significant, improvements in speech intelligibility in noise performance were reported by Sweetow and Sabes (2006) on the QuickSIN test (see Section 2.2.3 for a description of QuickSIN). These improvements were maintained 8 weeks post-intervention. Improvements were also seen on the Hearing in Noise Test (HINT) but these did not reach significance. Olson (2013) demonstrated improvement on the QuickSIN following LACE training with a large effect size (0.8) for experienced

Table 1. Summar	y of commonl	y used auditory	/ training programmes
-----------------	--------------	-----------------	-----------------------

Name	Aim	Format	Population	Stimuli	Adaptive	Time	Reference
Earobics	Improve spelling, reading and	Computerised	Children and adults	Recorded speech	Adaptive	15-20 minutes, 3 times per week	www.earobics.com
	language						
FastForWord	Improve speed of auditory language processing and reading abilities	Computerised	Children and adults	Speech and non- speech stimuli		30 minutes, 5 days per week, 3-4 months	www.innovative- therapies.com
Phonomena	Improve auditory discrimination, phonemic awareness and build language skills	Computerised	Children		Adaptive		www.mindweavers.com
Listening and Communication Enhancement (LACE)	Improving listening skills	Computerised	Adults	Stimuli: Speech - sentences Processes: speech in noise, cognitive tasks, compressed speech	Adaptive	20 minutes, 5 times per week, 4 weeks	Sweetow and Sabes (2006) www.laceuk.co.uk
Dichotic Inter- aural Intensity Difference	Improving binaural separation and integration	Non- computerised, normally in clinic	Children and Adults	Stimuli: speech - digits, CV pairs and sentences Task: dichotic listening	Difficulty level set by clinician	15-30 minutes, 3-4 times per week, 2-3 months	Weihing and Musiek (2007)
Differential Processing Training	Improving auditory awareness and attention, and language comprehension	Non- computerised, CD workbook	Children	Speech and non- speech stimuli Auditory process: Dichotic listening, temporal patterning, auditory discrimination	Increasing difficulty level		Wingett (2007)

hearing aid users such as those to be used in the present study. Song et al (2012) have also reported significant improvements on the QuickSIN and HINT tests following LACE training.

For a training programme to be considered successful, on-task training effects should be associated with improved functional performance. There is increasing emphasis on the importance of cognitive abilities in the maintenance of auditory performance (Rönnberg et al., 2008; Shinn-Cunningham and Best, 2008). Studies have shown the influence of working memory (Rönnberg et al, 2008) and selective attention (Shinn-Cunningham and Best, 2008) on auditory performance in challenging listening situations. A successful auditory training programme should show off-task learning effects on cognitive performance. Many auditory training programmes (including LACE) involve training on a number of different auditory and cognitive processes however there has been little research into the effect of auditory training on cognitive performance (Henshaw and Ferguson, 2013a). Sweetow and Sabes (2006) reported improvements on the Listening Span Test and Stroop Colour Word test which assess working memory and selective attention following LACE training however it is unknown which aspect of the training had the greatest effect on performance. Henshaw and Ferguson (2013b) showed improvement in performance on a competing speech task and a dual task of listening at a challenging SNR following a phoneme-discrimination-in-noise training task. The effect of auditory training on cognitive abilities warrants further research.

The effects of auditory training are thought to occur due to the neural plasticity evident in the human brain (Willott, 1996; Tremblay and Kraus, 2002; Tremblay, 2003; Song et al., 2012). Neural plasticity refers to "alterations in the physiological and anatomical properties of neurons in the brain in association with sensory stimulation or deprivation" (Tremblay and Kraus, 2002, p93). Sensory stimulation has been shown to bring about neural changes in the central auditory system in both animal (Recanzone et al., 1993) and human studies (Kraus et al., 1995; Ponton et al., 1996). Systemic changes in the central auditory system are associated with improvements in behavioural performance (Recanzone et al., 1993, Song et al., 2012). Song et al. (2012) found that changes in the auditory brainstem response, and the concomitant improvement in performance, following LACE training were retained at six months following the intervention showing that the anatomical and behavioural changes of auditory training are maintained long-term. Since sensory stimulation alone has been shown to induce neural alterations

(Ponton et al., 1996) it is theorised that repeated exposure to challenging stimuli should bring about changes in behavioural performance.

As well as the objective improvements listed above, there have also been improvements in self-reported hearing abilities following LACE training shown in the literature. Sweetow and Sabes (2006) found a reduction in reported handicap on the Hearing Handicap Inventory for the Elderly and improvement on the Communication Scale for Older Adults. The participants from Olson (2013) also reported a benefit on training measured using the International Outcome Inventory – Hearing Aids and International Outcome Inventory – Alternative Intervention questionnaires. However, no reported improvement was seen for these participants on the Speech, Spatial and Qualities of Hearing Questionnaire. While improvements on objective measures of speech perception and cognitive performance are important, the effects of these improvements on reported abilities in real-world listening environments are also key to improving the quality of life for patients with hearing loss.

2.2.3 Speech Intelligibility in Noise Objective Measure

The QuickSIN (Killion et al., 2004) was developed as a shortened and improved version of the Speech in Noise Test (Etymotic Research, Inc, 1993 cited in Killion et al., 2004). The QuickSIN includes 12 lists of six IEEE sentences which the participant has to repeat back. The sentences each contain five key words and are presented in four-talker babble. The QuickSIN is an adaptive test using a descending paradigm to establish the participant's signal-to-noise (SNR) loss. SNR loss is the dB increase in the signal-to-noise ratio required by the participant in order to identify 50% of the stimuli correctly relative to a person with normal hearing (Etymotic Research, Inc., 2006).

The QuickSIN may be used clinically to assess the benefit of amplification, or of different hearing aid features, on the patient's ability to understand speech in noise (Taylor, 2003). The QuickSIN has also been shown to be a sensitive tool for investigating the effects of auditory training on speech intelligibility in noise performance (Sweetow and Sabes, 2006; Olson et al., 2013). As discussed in Section 2.2.3 in a recent study by Olson et al. (2013) a large effect size (0.8) was shown on the QuickSIN for experienced hearing aid users following a period of LACE training. This recommends the use of this measure in the current study. The QuickSIN will be administered pre-and post-intervention to

investigate the effect of the training on participants' speech intelligibility in noise performance.

2.2.4 Self-report Measures

The Hearing Handicap Inventory for the Elderly (HHIE; Ventry and Weinstein, 1982a) will be used to evaluate the subjective effect of the training intervention. The HHIE is designed to assess the social and emotional impact of a hearing impairment on older adults. The questionnaire includes 25 questions and users are asked to mark each question "Yes", "No" or "Sometimes". The questionnaire is scored out of a possible 100, with 1-16 indicating no handicap, 17-42 indicating mild to moderate handicap, and 43-100 indicating significant handicap (Ventry and Weinstein, 1982b). Subtotal scores can also be calculated for emotional (12 items, maximum score 48) and situational items (13 items, maximum score 52). The HHIE is a highly reliable measure with good content validity (Ventry and Weinstein, 1982b). The tool is aimed at older adults aged 65 and over which makes it a relevant tool for use in the BCUHB population. As reported above in Section 2.2.2.2, significant improvements were shown on the HHIE following LACE training (Sweetow and Sabes, 2006). The use of the HHIE in the current study will enable comparison of results to previous research.

The Glasgow Hearing Aid Benefit Profile (Gatehouse, 1999) is commonly used throughout Audiology in both research and clinical practice. It assesses auditory disability, handicap and hearing aid benefit through by asking patients to rate their performance on four pre-set listening situations and up to four self-selected listening situations. Of particular interest in this study is the self-reported disability in the most challenging pre-set listening situation: Having a conversation with several people in a group. Previous research (Ferguson et al., in press) has used this question in isolation to assess the effect of an auditory training programme.

2.2.5 Cognitive measures

2.2.5.1 Competing Speech Task

The Modified Coordinate Response Measure (MCRM) is a measure of speech intelligibility based upon the Coordinate Response Measure described by Bolia et al (2000). The Coordinate Response Measure has been widely used in studies of

informational masking (Brungart, 2001; Eddins, 2012). The original task was designed for use in research with military personnel including call signs such as "Baron" or "Hopper" within the stimulus sentence. This study uses the modified task utilised by Henshaw and Ferguson (2013b) which replaces the call signs with animals. Stimuli take the form of "show the [animal] where the [colour] [number] is" with a total of six possible monosyllabic animals, six colours and eight numbers (1-9 excluding 7). Two sentences are spoken simultaneously by a female (target) or male (distractor) voice and participants are asked to identify the colour and number spoken by the female talker. The participant's speech reception threshold (SRT) is measured using an adaptive staircase method.

Henshaw and Ferguson (2013b) identified the MCRM as an outcome measure which is sensitive to the functional benefits seen on an auditory training task using phoneme discrimination in noise. Performance on the MCRM was correlated with self-reported listening difficulties and working memory performance (Henshaw and Ferguson, 2013b). This inclusion of this measure within the present study will enable the assessment of off-task learning effects of the training programme.

2.2.5.2 Dual Task of Listening and Memory

The dual task of listening and memory was designed to assess listening effort (Howard et al, 2010). It consists of a five digit memory task and a speech-in-noise repetition task. The method used in this study was described by Henshaw and Ferguson (2013b). Participants are asked to memorise five digits displayed visually. They are then given a list of five AB words (Boothroyd, 1968) presented in ICRA sic-talker babble at 0dB SNR and asked to repeat each word immediately. They are then asked to recall the original five digits. Henshaw and Ferguson (2013b) showed an effect of phoneme discrimination in noise training on the dual task in the challenging 0dB SNR condition when compared to performance in quiet or at -4dB SNR. There was evidence of altered resource allocation in this condition as there was a reduction in performance seen on both the digit recall and word repetition task in relation to the quiet condition. This reflects improvements in complex cognition following training. Henshaw and Ferguson (2013b) identified the dual task of listening and memory as a measure sensitive to the effects of auditory training when undertaken at a sufficiently challenging level (0dB SNR).

2.2.6 Gaps in Knowledge

- The proposed approach to auditory training (detailed in Section 2.5.6) has not previously been reported in the literature and therefore it is unknown whether this format of intervention will be effective in improving speech perception.
- It is also not known what the effect of this approach to auditory training will have on cognitive performance, which has been shown to be an important factor in understanding speech in background noise.

2.3 Research Questions

Primary – Does repeated practice improve speech perception in everyday challenging listening environments for experienced adult hearing aid users?

Secondary – Does repeated practice listening to speech in the presence of a competing speaker affect the cognitive performance of experienced adult hearing aid users?

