2.4 Hypotheses

H₀ - There will be no significant improvements in speech-intelligibility in noise, cognition and self-reported hearing abilities for experienced adult hearing aid users in either the experimental or control group.

H₁ - Auditory training will result in significant improvements in speech intelligibility in noise, cognition and self-reported hearing abilities of experienced adult hearing aid users (experimental group). These improvements will be significantly greater than for participants who do not receive the auditory training programme (control group).

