2.5.3 Research Design and Group Allocation

This study will be a randomised control trial investigating the effect of a repeated practice listening to speech in the presence of a competing speaker on a variety of outcome measures. Participants will be randomly assigned to either the control or training group. Randomisation will be carried out using a dynamic adaptive allocation algorithm (Hoare et al., 2013) with an allocation ratio of 1:1. Two stratification variables will be used for the randomisation: age (<75 years : \geq 75 years) and sex (male : female). The experimental group will carry out the training programme detailed in Section 2.5.6 while the control group will be given a placebo intervention.

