2.5.6 Training Programme

The training programme used in this study will focus primarily on improving speech perception in noise. Participants will have a conversation with their communication partner in the presence of a single competing speaker presented in soundfield for 30 minutes, five times per week for four weeks. The training schedule used in this study is based on the well documented regimen used in the LACE training programme. The single-talker distractor will be formed of a selection of 30 minute extracts from four English language commercially available audiobooks. A range of male and female distractors will be used. A single-talker distractor has been chosen as studies have shown that the informational masking from an intelligible single-talker has a greater effect on performance than the energetic masking from speech-shaped noise (Brungart, 2001). These extracts will be recorded onto a CD which will be provided to the participants in order for them to complete the training programme at home. At the end of each 30 minute extract a tone will sound to alert the participant that the training session for that day is complete. Participants will be instructed to play the CD at a level which is challenging but comfortable (i.e. not too loud).

As previously stated, compliance for clinically administered auditory training programmes has previously been low. In order to improve compliance a spoken letter will be given to the participants after the tone at the end of their training session. An incentive will be given to participants completing the training programme by being entered into a prize draw to win £25 book tokens for gathering all of the letters.

The placebo training programme undertaken by the control group will involve the same period of training but in quiet. They will be given a blank CD which is segmented into 30 minute sections with the tone and compliance letter given at the end of the training session.

All training, placebo and intervention, should be carried out while the participant is wearing their hearing aid/s. If the participant has multiple programs for different listening environments they should complete the training while listening in the program most suited to the training situation i.e. everyday listening for the control group and background noise for the experimental group.

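### The primary question asks about repeated practice in general, but both arms practise equally, so the randomised comparison estimates only what the competing speaker adds, and the hypotheses have no place for equal gains in both arms

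*Protocol*

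**What the plan says.** **The question.** Section 2.3 gives the primary question as "Does repeated practice improve speech perception in everyday challenging listening environments for experienced adult hearing aid users", and section 1.3 states it in the same words as the research question. Neither place mentions a competing speaker or a comparator. The secondary question, directly below in 2.3, is specific: "Does repeated practice listening to speech in the presence of a competing speaker affect the cognitive performance of experienced adult hearing aid users".

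**The design.** Section 2.5.3 describes a randomised trial "investigating the effect of a repeated practice listening to speech in the presence of a competing speaker" on a range of outcomes, in which "the control group will be given a placebo intervention".

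**The two programmes (2.5.6).** The training arm converses with a partner against a single competing talker "for 30 minutes, five times per week for four weeks". For the controls, "The placebo training programme undertaken by the control group will involve the same period of training but in quiet". They receive a blank CD in 30-minute segments with the same end tone and compliance letter. Hearing aids are worn in both arms. Users with several programs are advised to use a different one in each arm.

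**The hypotheses (2.4).** The null is that neither group improves. The alternative has two parts: the training group improves, and "These improvements will be significantly greater than for participants who do not receive the auditory training programme (control group").

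**The analysis (2.6.2).** An ANCOVA is to look for main effects of time or of group on every outcome.

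**The concern.** The question, the hypotheses and the analysis do not all address what is randomised. The unqualified question is about practice, yet practice is given in equal amount to both arms. The alternative hypothesis describes controls only by what they do not receive, and does not say that they complete a time-matched programme.

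The conclusion could go wrong in three ways:

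- **No group difference.** Read against the primary question as worded, this could be reported as practice not working. The trial would have shown only that adding a competing speaker made no detectable difference.
- **A group difference.** This could be credited to practice in general, when it shows the increment from the competing speaker.
- **Equal gains in both arms.** The null in 2.4 is then false and so is the second part of the alternative. A significant time effect could be used to reject the null and be presented as benefit from practice, although no arm without practice exists to separate it from retest and other before-after influences.

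The reading has consequences. Section 3.3 makes the offer of the programme to controls depend on whether it is found effective, and section 3.1.2 expects the results to inform wider use.

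**Working it through.** **1. Amount of practice by arm.** Input: the schedule in 2.5.6, which gives the control arm the same period.

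- Training arm: 5 sessions per week × 4 weeks = 20 sessions; 20 × 30 min = 600 min.
- Control arm: the same, 600 min.
- Randomised difference: 600 − 600 = 0 min.

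**2. What each contrast estimates.** Let g be the gain from conversation practice in quiet, d the further gain from the competing speaker (with the advised program), and r the before-after change that has nothing to do with practice, such as retest familiarity. Assume that these add up and that r is the same in both arms.

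| Quantity | Expected value |
|---|---|
| Change, training arm | g + d + r |
| Change, control arm | g + r |
| Difference between arms | d |
| Time effect averaged over 1:1 arms | g + r + d/2 |
| Unqualified primary question | g + d |

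The difference between arms is d alone. The time effect contains r, so it can be non-zero even when g = d = 0. Section 2.5.8 limits r in part: QuickSIN lists differ between visits, and the single and dual tasks are run twice at the first visit with only the second run scored. These steps reduce retest effects but do not remove familiarity with the tests.

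**3. Equal gains set against 2.4.** Put d = 0 and g + r > 0. Both arms improve, so the null (no improvement in either group) is false. The gains are equal, so the second part of the alternative is false. Neither hypothesis describes the result.

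**4. Could quiet practice do something?** The documents give no value for g. Section 3.1.1 says that involving the partner may prompt wider use of hearing tactics, and controls also have a partner. Section 2.2.2.2 says that stimulation alone can bring about neural change. Neither shows that quiet practice improves speech in noise, but they leave no ground for taking g as zero.

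**5. Sample size, for scale only.** The stated figure in 2.5.2 reproduces. With effect 0.8, two-sided 5% and 80% power, n = 2(1.960 + 0.842)² / 0.8² = 24.5, so 25 per group (power 81% by the normal approximation; the t-based calculation gives 25.5, so 26). Suppose, purely as an assumption, that 0.8 is the whole effect g + d and that quiet practice supplies a share f of it. Then d = 0.8(1 − f):

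| f | d | Power with 25 per group | n per group for 80% |
|---|---|---|---|
| 0 | 0.80 | 81% | 25 |
| 10% | 0.72 | 72% | 31 |
| 25% | 0.60 | 56% | 44 |
| 50% | 0.40 | 29% | 99 |
| 75% | 0.20 | 11% | 393 |

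The table does not show that 25 is wrong. It shows that a null between-arm result becomes more likely if quiet practice is active, which is when the wording of the question matters most.

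**The case against.** The strongest reply is that repeated practice is shorthand for the programme in 2.5.6. The sentence after the question in 1.3 defines the programme by its competing speaker. Section 2.1 sets the primary aim in terms of the training programme, 2.2.6 ties the gap in knowledge to the approach in 2.5.6, and 2.5.3 applies the competing-speaker wording to all outcomes. The rationale in 2.2.2.2 rests on exposure to challenging stimuli, which practice in quiet lacks. On that reading, a time-matched placebo is the right control for attention, contact and retest, and the comparison answers the intended question. The alternative hypothesis is also literally true, since controls do not receive the programme as 2.5.6 defines it.

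Most of this stands. A reader might infer from the primary question that the trial cannot answer what it set out to ask, or that the narrower wording is confined to the secondary question. The documents do not support either inference, because 1.3, 2.1, 2.2.6 and 2.5.3 identify the tested intervention well enough. A reader might also say that a null result would be misread. That predicts how the trial will be reported; the protocol shows only that it could be. Nor do the documents give any size for a quiet-practice effect.

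The reply does not reach the null hypothesis in 2.4 or the main effect of time in 2.6.2. However the question is read, equal gains in both arms have no defined interpretation, and a before-after change is among the planned tests.

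**Conclusion.** The point holds as a mismatch of wording and hypotheses, not as a flaw in the design. The primary question in 1.3 and 2.3 is wider than the randomised contrast. Both arms are scheduled for 600 minutes, and what differs is the competing speaker plus the advised hearing-aid program. The null in 2.4 and the time effect in 2.6.2 leave room for an uncontrolled before-after change to count as evidence for practice.

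This rests on reading the control activity in 2.5.6 as partner conversation on the same schedule without the competing talker, which is the natural reading of that section. It does not depend on any value for the effect of quiet practice; the power range above is illustration under an assumption. No figure in the protocol is shown to be wrong, and the matched control should not be counted as an error. The point is worth settling before results exist, because it determines what the trial may conclude in either direction.

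**What to change.** Keep the comparator and change the text as follows.

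- **1.3 and 2.3:** align the primary question with 2.5.3. For example: does four weeks of conversation practice with a competing speaker improve speech intelligibility in noise more than the same amount of conversation practice in quiet?
- **2.4, null:** restate it as no difference between the groups.
- **2.4, alternative:** describe controls as completing the same practice in quiet.
- **2.6.2:** base the efficacy conclusion on the between-group comparison alone, and report change over time within arms descriptively.
- **Interpretation:** state that a null between-arm result does not show practice itself to be ineffective.

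Nothing changes in allocation, treatment, visits or data collection. The cost is a narrower claim and the loss of the within-group test in the first sentence of the alternative hypothesis, with the time effect no longer serving as evidence of efficacy.
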